10.1.4 SAEs

An SAE is defined as any untoward medical occurrence that at any dose:

CONFIDENTIAL

1. Results in DEATH.
2. Is LIFE THREATENING.*
3. Requires inpatient HOSPITALIZATION or prolongation of existing hospitalization.
4. Results in persistent or significant DISABILITY/INCAPACITY.
5. Leads to a CONGENITAL ANOMALY/BIRTH DEFECT.
6. Is an IMPORTANT MEDICAL EVENT that satisfies any of the following:
 - May require intervention to prevent items 1 through 5 above.
 - May expose the subject to danger, even though the event is not immediately life threatening or fatal or does not result in hospitalization.
 - Includes any event or synonym described in the Takeda Medically Significant AE List ([Table 10.a](#)).

* The term “life threatening” refers to an event in which the subject was at risk of death at the time of the event; it does not refer to an event that hypothetically might have caused death if it were more severe.

Table 10.a Takeda Medically Significant AE List

Term	
Acute respiratory failure/acute respiratory distress syndrome (ARDS)	Hepatic necrosis
Torsade de pointes / ventricular fibrillation / ventricular tachycardia	Acute liver failure
Malignant hypertension	Anaphylactic shock
Convulsive seizure (including seizure and epilepsy)	Acute renal failure
Agranulocytosis	Pulmonary hypertension
Aplastic anemia	Pulmonary fibrosis (including interstitial lung disease)
Toxic epidermal necrolysis/Stevens-Johnson syndrome	Neuroleptic malignant syndrome / malignant hyperthermia
	Spontaneous abortion / stillbirth and fetal death
	Confirmed or suspected transmission of infectious agent by a medicinal product
	Confirmed or suspected endotoxin shock

The following events are also to be considered SAEs.

- Completed suicide
- Active suicidal ideation
- Active suicidal behavior such as suicide attempt
- Self-injury with suicide attempt

PTEs that fulfill 1 or more of the serious criteria above are also to be considered SAEs and should be reported and followed up in the same manner (see Sections [10.2.2](#) and [10.3](#)).

10.1.5 Special Interest AEs

A Special Interest Adverse Event (serious or non-serious) is 1 of scientific and medical concern specific to the compound or program. In this study, skin reaction, allergic reaction, hepatic impairment, and overdose are defined as special interest AEs. Ongoing monitoring and communication by the investigator to Takeda may be appropriate, and if the events occur, they will be reported according to Section [10.2.1.3](#). Such events may require further investigation in order to characterize and understand them.

10.1.5.1 Skin and Allergic Reaction

When the causal relationship between rash or allergic reaction and the study medication is assessed as probable or possible, rash or allergic reaction will be reported as a special interest AE according to Section [10.2.1.3](#) after the nature and the site are characterized. When the causal relationship between rash or allergic reaction and the study medication is assessed as not related, rash or allergic reaction is not required to be reported as a special interest AE.

When rash or allergic reaction develops, the subject should be adequately examined for any clinical features that may suggest the development of drug reaction with eosinophilia and systemic symptoms (DRESS), toxic epidermal necrolysis (TEN), or Stevens-Johnson syndrome (SJS). In addition, the subject should be monitored for the appearance of any of the following signs:

- a) Involvement of mucous membrane or the conjunctiva
- b) Development of skin pain
- c) Urticaria, blistering, or other types of skin lesions
- d) Angioedema

If a subject presents with symptoms of a systemic reaction (e.g., generalized rash), or signs of severe rash, or if it is clinically necessary, the following laboratory parameters should also be investigated and monitored accordingly: complete blood count with differentials, liver and renal function tests, and urinalysis. If deemed necessary by the investigator, subjects should be received examination by a dermatologist, and photographs of the skin rash and/or skin biopsies will be obtained as needed.

10.1.5.2 Hepatic Impairment

If a subject has ALT or AST $>3 \times$ ULN, and follow-up laboratory tests (see Section [9.1.12](#)) also shows ALT or AST $>3 \times$ ULN, it should be reported as a special interest AE according to Section [10.2.1.3](#). In addition, the relevant subject details and possible alternative etiologies other than the study medication should be investigated.

If the abnormality falls under a drug-induced liver function abnormality that may lead to severe hepatic impairment (see Section 10.2.3), it should also be reported as an SAE.

10.1.5.3 Overdose

For overdose, refer to Section 8.1.4. All cases of overdose will be documented as AEs on an AE page of the eCRF and should be reported as special interest AEs according to Section 10.2.1.3 (with or without associated adverse events).

10.1.6 Severity of PTEs and AEs

The different categories of intensity (severity) are characterized as follows:

Mild:	The event is transient and easily tolerated by the subject.
Moderate:	The event causes the subject discomfort and interrupts the subject's usual activities.
Severe:	The event causes considerable interference with the subject's usual activities.

10.1.7 Causality of AEs

The relationship of each AE to study medication(s) will be assessed using the following categories:

Probable:	An AE that has a strong temporal relationship to the study medication(s), or recurs on re-challenge, and another etiology is unlikely or significantly less likely.
Possible:	An AE that has a suggestive temporal relationship to the study medication(s), and an alternative etiology is equally or less likely.
Not Related:	An AE that does not follow a reasonable temporal sequence from administration of the study medication(s) or that can reasonably be explained by other factors, such as underlying diseases, concurrent medical conditions, concomitant drugs and concurrent treatments (that is, there is no causal relationship between the study medication and the AE).

An AE is considered causally related to the use of the study medication when the causality assessment is *probable* or *possible*.

10.1.8 Relationship to Study Procedures

Relationship (causality) to study procedures should be determined for all PTEs and AEs. The relationship should be assessed as Related if the investigator considers that there is reasonable possibility that an event is due to a study procedure. Otherwise, the relationship should be assessed as Not Related.

10.1.9 Start Date

The start date of AEs/PTEs will be determined based on the criteria described below.

AE/PTE	Start Date
Signs, symptoms, and diseases (diagnosis)	Date when the subject or the investigator first notices the sign or symptom of the AE
Asymptomatic disease	Date when a definite diagnosis is determined based on the results of diagnostic testing. Even if obsolete findings are indicated based on the test findings or the approximate time of onset can be estimated, the date when a definite diagnosis is made should be recorded.
Worsening of concurrent medical conditions or PTEs	Date when the subject or the investigator first notices worsening of the disease or symptom.
Normal in the initial assessment after signing of informed consent but abnormal in the subsequent assessment (for PTEs) Abnormal in the assessment after the start of the study medication (for AEs)	Date when the test is performed in which a clinically significant abnormal test value is observed
Abnormal in the initial assessment after signing of informed consent and has worsened in the subsequent assessment (for PTEs) Abnormal in the assessment at the start of the study medication and has worsened in the subsequent assessment (for AEs)	Date when the test is performed in which a medically significant elevation, reduction, increase or decrease in clinical laboratory test values is observed

10.1.10 Stop Date

The stop date of the AE/PTE is the date at which the subject recovered, the event resolved but with sequelae or the subject died. The AE/PTE not determined to have resolved at the end of the study is assessed as ongoing

10.1.11 Frequency

Episodic AEs/PTEs (e.g., constipation, diarrhea, vomiting) or those which occur repeatedly over a period of consecutive days are intermittent. All other events are continuous.

10.1.12 Action Concerning Study Medication

The action taken for the study medication is classified and defined as follows:

Drug withdrawn	The study medication is stopped due to the particular AE (including withdrawal at the subject's discretion).
Dose not changed	The dose is not changed even after the occurrence of the particular AE. This shall apply in case the study medication is stopped due to another AE. This shall also apply, for example, in case the study medication is stopped for any reason other than intervention for the particular AE, such as the subject's negligence.

Unknown	For example, attempts to contact the subject are unsuccessful and the course of the particular AE after the start date cannot be followed.
Not Applicable	For example, the study medication has already been completed or stopped before the onset of the particular AE.

10.1.13 Outcome

The outcome of AEs/PTEs is classified as follows:

Category	Assessment Criteria
Recovered/Resolved	
 The symptom or finding has disappeared or resolved. The abnormal laboratory value has improved to the normal range or to the level at baseline (for AEs) or at the first assessment after signing of informed consent (for PTEs).
Recovering/Resolving	
 The intensity is lowered by at least 1 grade. The symptom or finding has almost disappeared. The abnormal laboratory value has improved, but not to the normal range or the level at baseline (for AEs) or at the first assessment after signing of informed consent (for PTEs). The subject died from a cause other than the particular AE/PTE with the condition remaining “recovering/resolving” (no need to record the date of death).
Not recovered/not resolved	
 There is no change in the symptom, finding, or laboratory value. The intensity of the symptom, finding, or laboratory value on the last day of the observed period has got worsen than when it started. An irreversible congenital anomaly. The subject died from another cause with the particular AE/PTE state remaining “Not recovered/not resolved” AE/PTE (no need to record the date of death).
Resolved with sequelae	
 The subject recovered from an acute AE/PTE but was left with impairment that interferes with the subject’s daily life.
Fatal	
 There is a direct relationship between the death and the AE/PTE. The direct relationship indicates that the AE/PTE caused or apparently contributed to the death. The outcome of another AE/PTE reported in the same subject that is not determined (considered or estimated) as the cause of the death is not assessed as “fatal.” If the outcome is “fatal,” the date of death should be recorded.
Unknown	
 The course of the AE/PTE after the start date cannot be followed up as specified in the protocol due to hospital change or residence change.

10.2 Procedures

10.2.1 Collection and Reporting of AEs

10.2.1.1 PTE and AE Collection Period

Collection of PTEs will commence from the time the subject signs the informed consent to participate in the study and continue until the subject is first administered study medication in the

placebo lead-in period. For subjects who discontinue prior to the first study medication administration in the placebo lead-in period, PTEs are collected until the subject discontinues study participation.

Collection of AEs will commence from the time that the subject is first administered study medication in the placebo lead-in period. Routine collection of AEs will continue until Visit 8 or Early Termination Visit.

Collection of SAEs or special interest AEs will continue until the end of the follow-up period.

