4.1.1 Clinical Pharmacology

Results of clinical pharmacology studies in Japan and overseas are summarized below.

Lu AA21004 was slowly absorbed after oral administration, and the Tmax was approximately 7 to 11 hours. The absolute bioavailability of Lu AA21004 was approximately 75%. The

pharmacokinetics of Lu AA21004 was linear within the dose range between 2.5 and 60 mg. The plasma concentration of Lu AA21004 reached steady state after approximately 2-week multiple doses, and the accumulation index was 5 to 6 based on AUC following multiple doses of 5 to 20 mg/day. There was no food effect on the pharmacokinetics of Lu AA21004.

Lu AA21004 was extensively metabolized in the liver, primarily through oxidation or glucuronic acid conjugation, and CYP2D6 was shown to be the primary enzyme in metabolism of Lu AA21004 to the major metabolite Lu AA34443. Lu AA34443 was pharmacologically inactive, and the active metabolite Lu AA39835 did not cross the blood-brain barrier, although Lu AA39835 was slightly detected in plasma, suggesting that these metabolites are less likely to contribute to the pharmacological effect of Lu AA21004. In addition, Lu AA21004 and its metabolites did not induce or inhibit CYP isozymes *in vitro*, suggesting that clinical significant drug-drug interactions with Lu AA21004 are less likely to occur.

The T1/2 of Lu AA21004 was approximately 66 hours, and two- thirds of its metabolites were excreted in urine, and one-third were excreted in feces. The excretion of unchanged Lu AA21004 was slightly noted in feces.

After multiple doses of Lu AA21004, 5-HTT occupancy in raphe nuclei was approximately 50% at doses of 5 mg/day, 65% at 10 mg/day, and 80% or more at 20 mg/day.

Based on results of studies in Caucasian and Japanese subjects, there were no statistically significant differences in the pharmacokinetics and 5-HTT occupancy of Lu AA21004 between the races.

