4.1.2 Overseas Phase II/III Clinical Studies

A total of 12 overseas placebo-controlled, double-blind, short-term studies (Studies 11492A, 11984A, 303, 304, 305, 13267A, 315, 316, 317, CCT-002, 12541A and 14122A) were conducted to evaluate the efficacy of Lu AA21004 for the treatment of MDD. Study CCT-002 was a multinational study including Japan.

The changes from baseline in the Montgomery-Åsberg Depression Rating Scale (MADRS) total score were analyzed by mixed model repeated measures (MMRM) in the individual studies; and the results of the 11 of 12 studies mentioned above except for Study 12541A for elderly patients were used for meta-analysis. As for the mean changes from baseline in the MADRS total score at Week 6 or 8, the differences of the Lu AA21004 5, 10 and 20 mg group compared to the placebo group were -2.3 (p = 0.007), -3.6 (p < 0.001) and -4.6 (p < 0.001), respectively, and all of them were statistically significant. In addition, although the mean difference between the 15 mg group and placebo group was -2.6, not statistically significant. MADRS response rate (MADRS response is defined as a \geq 50% decrease from baseline in the MADRS total score) in the subjects treated with Lu AA21004 was 46% to 49%, whereas that in the subjects treated with placebo was 34% (p < 0.01). These results suggested Lu AA21004 at doses of 5 to 20 mg/day was effective.

For comprehensive safety evaluation including the above-mentioned short-term studies and long-term studies (Studies 11492C, 11984B, 301, 13267B and 314), treatment with Lu AA21004 at doses of 5 to 20 mg/day was safe and well tolerated. The most common TEAE in the

Lu AA21004 groups was nausea, and gastrointestinal TEAEs were occurred more frequently in female than male. Most TEAEs were mild or moderate and occurred within the first 2 weeks of treatment. In addition, TEAEs were usually transient, and did not generally lead to discontinuation of the study medication.

Abrupt discontinuation of antidepressants may result in discontinuation symptoms, however, there were no clinically relevant differences in the incidence or nature of discontinuation symptoms between the Lu AA21004 groups and placebo group.

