9.3.6 Follow-up Period

A safety follow-up assessment will be conducted at 12 weeks after the start of double-blind treatment period (Day 84 ± 5). For subjects who prematurely discontinue the study during the placebo lead-in period or double-blind treatment period, the follow-up assessments will be made 28 ± 5 days after the last dose of the study medication. The follow-up assessments may either be conducted as a visit to the site or as a telephone contact. In the follow-up, the following will be assessed: outcomes of AEs continuing at Visit 8 or early termination visit, new SAEs developing during the follow-up period, and special interest AEs will be assessed. Female subjects of child-bearing potential will be asked to confirm whether they are pregnant or not.

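### New non-serious adverse events outside the special interest list are not routinely collected after Visit 8 or early termination, so completers' off-drug symptoms go largely unsolicited; the existing follow-up contact could close this cheaply

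*Protocol*

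**What the plan says.** Protocol Section 10.2.1.1 sets two end points for collection. For ordinary events: "Routine collection of AEs will continue until Visit 8 or Early Termination Visit". For the rest: "Collection of SAEs or special interest AEs will continue until the end of the follow-up period". Section 10.1.5 fixes the scope of the second group: "skin reaction, allergic reaction, hepatic impairment, and overdose are defined as special interest AEs". These may be non-serious as well as serious.

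Section 9.3.6 gives the content of the follow-up contact (Day 84 ± 5 for completers; 28 ± 5 days after the last dose for early terminators): "outcomes of AEs continuing at Visit 8 or early termination visit, new SAEs developing during the follow-up period, and special interest AEs will be assessed". Pregnancy status is also asked. Appendix A footnote (d) agrees.

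Sections 6.1 and 8.1.3 keep the assigned dose running to Week 8 and describe no step-down. Section 9.3.7 provides no drug afterwards. Section 4.1.1 states: "The T1/2 of Lu AA21004 was approximately 66 hours". Section 4.1.2 states: "Abrupt discontinuation of antidepressants may result in discontinuation symptoms". The same sentence adds that the active and placebo groups did not differ in a clinically relevant way in such symptoms.

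The SAP glossary starts the treatment-emergent period at the first double-blind dose and gives it no end. SAP Section 3.1.2 has an onset interval from Day 57 to the maximum.

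**The concern.** A secondary objective is the safety and tolerability of both doses in Japanese patients (Section 5.1.2), and Section 4.2 says further data may improve the safety evaluation. The background names symptoms on abrupt stopping as possible for the drug class. Yet for completers, routine questioning ends at about the last dose, before most of the drug has cleared. A completer who develops dizziness, insomnia or irritability on Day 60 is not asked about it.

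The same applies to suicidal thoughts that do not meet the serious definition. Section 10.1.3 makes these non-serious events, and the C-SSRS is last given at Visit 8 or early termination (Appendix A). This is relevant because the Japan local study, CCT-003, reported suicidal ideation in 6.6% at 10 mg against 1.6% on placebo (Section 4.1.3).

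Collection also depends on disposition. The early termination visit may come up to 7 days after discontinuation and includes a full event assessment. Early off-drug events in those subjects can therefore enter the treatment-emergent tables, while the same events in completers mostly cannot.

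**Working it through.** **1. Inputs.** Half-life 66 h, steady state at about 2 weeks, accumulation index 5 to 6 (Section 4.1.1). Visit 8 on Day 56 ± 3, and early termination visit within 7 days (Section 9.3.5). Follow-up contact on Day 84 ± 5 (Section 9.3.6).

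**2. Check on the half-life.** Five half-lives are 5 × 66 / 24 = 13.75 days, against about 14 days stated, so the figure is reproduced. One-compartment accumulation is 1 / (1 − 2^(−24/66)) = 4.49, below the stated 5 to 6. Solving half-life = 24 × ln 2 / −ln(1 − 1/R) gives 75 h for R = 5 and 91 h for R = 6. These serve as a sensitivity range.

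**3. Drug level remaining,** as a share of the level at the last dose: 2^(−24d / half-life).

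| Days since last dose | 66 h | 75 h | 91 h |
|---|---|---|---|
| 0 | 100% | 100% | 100% |
| 1 | 78% | 80% | 83% |
| 3 | 47% | 51% | 58% |
| 7 | 17% | 21% | 28% |
| 14 | 2.9% | 4.4% | 7.8% |
| 28 | 0.09% | 0.2% | 0.6% |

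I assume that a completer's last dose is on the day of Visit 8 or the day before. Then 78% to 100% remains when routine collection ends. If dosing stopped strictly after Day 56 and Visit 8 fell on Day 59, 3 days would have passed and 47% would remain.

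**4. Length of the gap for completers.** Nominal: 84 − 56 = 28 days. Shortest: 79 − 59 = 20. Longest: 89 − 53 = 36. At 66 h the level reaches 5% at 11.9 days (13.4 to 16.4 days at 75 to 91 h), well inside even the shortest gap.

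**5. Early terminators.** A visit 7 days off drug finds 17% remaining (21% to 28% at 75 to 91 h), so the first part of their washout is covered.

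**6. What is collected after Visit 8 or early termination.**

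| Event | Collected to follow-up? |
|---|---|
| Serious event, including active suicidal ideation (10.1.4) | Yes |
| Special interest event, serious or not | Yes |
| Outcome of an event already ongoing | Yes |
| Any other new non-serious event | Not routinely; only if the subject volunteers it (10.2.1.2) |

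**7. Scale.** The documents give no rate of discontinuation symptoms. As an assumption only: if all 160 subjects in an arm complete, true rates of 1%, 2% and 5% mean 1.6, 3.2 and 8 subjects per arm who are not asked about their event.

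**The case against.** The strongest reply is that the sponsor gave a reason to limit collection. The sentence that names discontinuation symptoms also reports no clinically relevant difference from placebo in earlier studies. No discontinuation endpoint is set, the secondary objective is worded around 8 weeks of treatment, and the protocol nowhere says that the follow-up exists to detect withdrawal effects. All of this stands, and it makes the point an improvement rather than an error. It does not supply the missing off-drug data in this population.

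A reader might infer that all non-serious collection stops, or that nothing off-drug is recorded. The documents do not support that. Section 10.1.5 says: "A Special Interest Adverse Event (serious or non-serious) is 1 of scientific and medical concern specific to the compound or program", and such events are collected to the end of follow-up. So are serious events, which include active suicidal ideation, and the outcomes of ongoing events. Subjects may also volunteer events at any time, although how that fits with the end of routine collection is not spelled out.

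It is also fair that the residual-drug percentages describe washout, not missed events, and that placebo subjects have no active drug to clear. And a separate table alone would not be enough: with an open-ended treatment-emergent definition, newly collected events would enter every treatment-emergent table. Standard therapy may start after Visit 8 (Section 9.3.5), while concomitant medication is recorded only to that visit (Section 9.1.10), so attribution would be weak. The fix has to deal with both.

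**Conclusion.** The gap is real and narrow. For completers, new non-serious events outside the four special interest categories are not routinely asked about for a nominal 28 days (20 to 36), which contains nearly all of the washout. Early terminators may have up to 7 off-drug days covered. The trial can therefore neither confirm nor contradict, in Japanese subjects, the overseas studies' result of no relevant difference from placebo on stopping. Few or no recorded symptoms after Visit 8 would partly reflect the collection rule.

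This rests on first-order elimination at the stated half-life and on a last dose within about a day of Visit 8. The sensitivity range does not change it.

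A reader might go further and infer that a known harm is being missed, or that the efficacy result or completers' on-treatment safety data are compromised. Nothing in the documents shows either. No sample size, power or type I error depends on this, and nothing here bears on how treatment should be stopped. It is a worthwhile, low-cost improvement.

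**What to change.** **Protocol.** In Sections 10.2.1.1 and 9.3.6 and Appendix A footnote (d), extend collection of all new adverse events to the existing follow-up contact, using the neutral question of Section 10.2.1.2. In Section 9.1.10, record medication started after Visit 8 or early termination up to that contact.

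**SAP.** In the glossary, state an end to the treatment-emergent period that applies in the same way to completers and early terminators, and set it before unblinding. Adjust the Day 57 to maximum interval in Section 3.1.2 to match. Its denominator counts only subjects with exposure or an event in or after the interval, so off-drug events placed there would give inflated percentages. Tabulate later-onset events by arm in a separate descriptive post-treatment table, with newly started medication shown alongside.

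**Cost.** One question at a contact that already takes place in every arm, a longer eCRF date range for events and medication, one definition and one table. No added visit.

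**Downside.** Events are recalled over about 28 days. Some will reflect newly started therapy. Events first found at the last contact may need some further follow-up under Section 10.2.1.2.
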